14.1.3 Secondary Analyses

Tumor assessments by IRC vs Investigator assessment

A summary of the IRC assessment versus Investigator assessment in terms of OR will be provided including numbers of concordant and discordant assessments. Concordance is established if the same result in terms of OR (OR achieved: Yes/No) can be reached regardless of whether the IRC or the Investigator assessments are used; on the contrary, different OR results indicate discordance. For OR based on Investigator assessment, see Section 14.2.1.

14.1.4Subgroup Analyses

Subgroup analyses will be performed on the primary endpoint for all the baseline subgroup levels defined in Section 8.2. Results will be presented for the combination arm only. All subgroup analyses are exploratory and no adjustment for multiplicity will be performed.

For each subgroup, the BOR, the number of participants achieving objective response, the ORR along with the two-sided exact Clopper-Pearson 95% CIs will be presented.

Forest plots will be created to graphically present ORRs and corresponding 95% CIs.

All subgroup analyses will be based on the mFAS.

14.2 Secondary Endpoints

14.2.1 Objective Response by Investigator assessment

BOR and OR based on Investigator assessment will be derived and analyzed as described for the primary endpoint based on IRC assessment (see Section 14.1.1).

The subgroup analysis as described in Section 14.1.1 as well as the sensitivity analysis based on FAS described in Section 14.1.2 will also be repeated based on Investigator assessments.

14.2.2 Confirmed CR by IRC and by Investigator

Participants are identified as having a confirmed CR if they achieve a confirmed CR from first administration of study treatment to first observation of PD, as described in Section 14.1.1.

Complete response rate (confirmed CR) and the corresponding 2-sided exact Clopper-Pearson 95% CI will be presented by IRC and by Investigator. Complete response rate will also be presented by subgroup.

The sensitivity analyses described in Section 14.1.2 will also be performed.

14.2.3 Duration of Response by IRC and by Investigator

Duration of Response (DOR) will only be evaluated for participants with objective response (as defined in Section 14.1.1).

DOR is the time from when the CR/PR (whichever is first) criteria are first met until PD or death due to any cause, within 126 days of the last evaluable tumor assessment, whichever occurs first (see Eisenhauer EA, et all 2009) (i.e., date of PD/death - date of last evaluable tumor assessment \leq 126).

DOR data will be censored on the date of the last evaluable tumor assessment for participants who do not have an event (PD or death) or for participants with an event more than 126 days after the last evaluable tumor assessment (i.e. date of PD/death - date of last evaluable tumor assessment > 126).

The last evaluable tumor assessment is defined as the last tumor assessment result that is not "NE".

Kaplan-Meier estimates (product-limit estimates) will be presented together with a summary of associated statistics for duration of response: median and corresponding two-sided 95% confidence interval (CI), Q1 and Q3, minimum and maximum. Progression-free rate estimates at 3, 6, 9, 12, 15, 18 months and for every 3 months thereafter as applicable including the corresponding two-sided 95% CIs will also be reported. The CI for the median will be calculated according to Brookmeyer and Crowley (1982) and CIs for the survival function estimates at the above defined time points will be derived using the log-log transformation according to Kalbfleisch and Prentice (1980) (conftype=loglog default option in SAS Proc LIFETEST). The estimate of the standard error will be computed using Greenwood's formula. Kaplan-Meier plots will also be presented.

Categorical summaries of DOR features will be presented for the following items:

- Number of participants with OR
- Duration of response: ≥ 6 months, ≥ 9 months, ≥ 12 months
- Follow-up among responders:
 - \circ participants with ≥ 6 months follow-up from onset of response or event (PD or death) or discontinued treatment < 6 months after onset of response
 - \circ participants with ongoing response with < 6 months duration

Results for DOR as described above will be presented by IRC and Investigator assessments.

Time to and duration of response for every participant will be plotted using a swimmer plot; results will be presented by IRC and by Investigator. Color coded symbols will be used to show the time of the following events: CR, PR, PD, death, ongoing response and end of treatment.

Sensitivitiy analyses

DOR and summary of DOR tables by IRC and Investigator will also be presented for the FAS for both treatment arms overall (i.e., with no split by MET amplification test result).

Subgroup analyses

The Kaplan-Meier based analysis described above will be repeated for all the baseline subgroups identified in Section 8.2. Tables and Kaplan-Meier plots of DOR stratified by these subgroups will be provided. Results will be presented for the combination arm only. The same rules described in the first paragraph of Section 14.1.4 will apply.

Follow-up for duration of response

In order to assess the follow-up for DOR, Kaplan Meier estimates will be calculated reversing the DOR censoring and event indicators.

Kaplan-Meier estimates (product-limit estimates) will be presented in the same way as in the analysis described above for DOR for both IRC and Investigator assessments.

14.2.4Disease control (confirmed CR + PR or SD lasting at least
12 weeks) by IRC and by Investigator

Participants are identified as having objective disease control (DC) if they achieve either a confirmed CR or PR (as defined in Section 14.1.1), or SD lasting at least 12 weeks (84 days).

DC rate, which is the proportion of participants with DC, and the corresponding two-sided exact Clopper-Pearson 95% CI will be presented by IRC and by Investigator. DC rate will also be presented by subgroup.

The sensitivity analyses described in Section 14.1.2 will also be performed.

14.2.5 Progression Free Survival by IRC and by Investigator

PFS time is defined as the time (in months) from first administration of study treatment to the date of the first documentation of PD or death due to any cause within 126 days of the last tumor assessment, whichever occurs first (i.e., date of PD/death - date of last evaluable tumor assessment \leq 126).

PFS data will be censored on the date of the last evaluable tumor assessment for participants who do not have an event (PD or death) or for participants with an event more than 126 days after the last tumor assessment (i.e. date of PD/death - date of last evaluable tumor assessment > 126).

The last evaluable tumor assessment is defined as the last tumor assessment result that is not "NE".

Participants who do not have an evaluable post-baseline tumor assessment will be censored at the date of the start of study treatment unless death occurred within 126 days of the first dose of study treatment in which case the death will be considered an event.

If a participant has only not evaluable tumor assessments prior to a PD which is within 126 days of the first dose of study treatment, the PD will be considered an event; if the PD is after the 126 days, the PFS will be censored at the date of first dose.

The censoring and event date options to be considered for the PFS are presented in Table 6.

Table 6. Date of event / censoring definition for PFS analysis

Status		Censoring	Date of event / censoring
Progressed or died	Within 126 days after last response assessment of CR, PR or SD or start of treatment	Event	Minimum (Date of PD, Date of death)
	Otherwise	Censored	Date of last tumor assessment with outcome CR, PR or SD or date of the start of treatment, whatever is later
Neither progress	sed nor died	Censored	Date of last tumor assessment with outcome CR, PR or SD or date of the start of treatment, whatever is later

60/94

Kaplan-Meier product-limit estimates will be presented together with a summary of associated statistics for PFS: median and corresponding two-sided 95% confidence interval (CI), Q1 and Q3, minimum and maximum. Progression-free rate estimates at 3, 6, 9, 12, 15, 18 months and for every 3 months thereafter as applicable including the corresponding two-sided 95% CIs will also be reported. The CI for the median will be calculated according to Brookmeyer and Crowley (1982) and CIs for the survival function estimates at the above defined time points will be derived using the log-log transformation according to Kalbfleisch and Prentice (1980) (conftype=loglog default option in SAS Proc LIFETEST). The estimate of the standard error will be computed using Greenwood's formula. Kaplan-Meier plots will also be presented.

Results for PFS as described above will be presented by IRC and Investigator assessments.

The above analyses for PFS will be repeated considering the start of any other anti-cancer treatment as PD (see Section 14.1.2). This sensitivity analysis will be based on IRC assessments.

The censoring and event status with respect to PFS and based on IRC assessments will be summarized.

Subgroup analyses

Subgroup analyses as described for DOR in Section 14.2.3 will be repeated for PFS.

PFS event: IRC versus Investigator

A summary of the IRC assessment versus Investigator assessment in terms of PFS will be provided including numbers of concordant and discordant assessments.

Follow-Up Duration of PFS

In order to assess the follow-up duration of PFS, Kaplan Meier estimates will be calculated reversing the PFS censoring and event indicators.

Kaplan-Meier estimates (product-limit estimates) will be presented in the same way as in the analysis described above for PFS for both IRC and Investigator assessments.

14.2.6Overall Survival

Overall survival (OS) time is defined as the time (in months) from the first administration of study treatment to the date of death.

For participants not known to be deceased at time of analysis or who died after the cut-off date, OS time will be censored at the date of last contact before data cut-off date as defined in Section 9.7.

The Kaplan-Meier based analysis described in Section 14.2.5 for the derivation of progression-free related estimates will be repeated for the survival related estimates.

The censoring and event status with respect to OS will be summarized.

OS analysis will be performed on the combination arm only.

Subgroup analyses

Subgroup analyses as described for DOR in Section 14.2.3 will be repeated for OS.

Follow-Up Duration of OS

In order to assess the follow-up duration of OS, Kaplan Meier estimates will be calculated reversing the OS censoring and event indicators.

Kaplan-Meier estimates (product-limit estimates) will be presented in the same way as in the analysis described above for OS.

This analysis will be performed on the combination arm only.

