8.1 Efficacy Assessments and Procedures

Complete tumor assessment of all lesions by radiographic modality (using RECIST Version 1.1) is required. CT or MRI of the chest and abdomen (including imaging of the whole of the liver and adrenal glands), must be conducted to evaluate disease in these locations. Additional anatomical areas, such as the pelvis or other body areas in question, should be investigated in case of suspicion of presence of metastases based on signs, symptoms, biochemical results and/or non-study imaging of individual participants.

In addition, all participants must have brain imaging by MRI with IV contrast enhancement, including T2/FLAIR sequences of the brain, at Screening and at Follow-up in participants with brain metastases confirmed by IRC on the baseline brain scan. For participants who are enrolled in the study and present with brain metastasis when possible, the MRI assessment shall include Coronal 3D Gd-T1WI, Axial TSE/T2WI, Axial FLAIR, Axial T1WI, Axial Gd-T1WI, and Coronal 3D Gd-T1WI. MRI may be performed without contrast enhancement, if contrast is contraindicated. At Screening and during the Follow-up visits, if brain MRI is not clinically feasible, CT of the brain with IV contrast enhancement may be used; CT may be performed without contrast enhancement, if contrast is contraindicated.

During the follow-up, tumors will be assessed every 6 weeks (\pm 7 days) following the Cycle 1 Day 1 visit until 9 months, and every 12 weeks (\pm 14 days) thereafter according to RECIST Version 1.1, until disease progression as per Investigator, death, study withdrawal, or withdrawal of consent. Both IRC and Investigator assessments will be conducted. For participants in the randomized part of the study, verification of disease progression by IRC is required. The same method of assessment and the same technique should be used to characterize each identified and reported lesion at Baseline and during the study. Tumor assessment according to RECIST Version 1.1 at EoT Visit is requested only if last tumor assessment was performed \geq 6 weeks within the first 9 months, or \geq 12 weeks after 9 months prior to EoT Visit.

When a pleural effusion occurs as an adverse event and is punctured, cytology should be evaluated for malignancy and the results communicated to the IRC for consideration of their assessment, as outlined in the IRC charter.

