9.6 Conversion Factors

The following conversion factors will be used to convert days into weeks, months or years:

- 1 week = 7 days
- 1 month = 30.4375 days
- 1 year = 365.25 days

If height is recorded in inches, height (cm) = height (in) \times 2.54.

If weight is recorded in pounds, weight $(kg) = weight (lb) \div 2.2046$.

For the calculation of creatinine clearance: serum creatinine (mg/dL) = serum creatinine (umol/L) / 88.42.

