9.11 Tumor Evaluation and Adjudication

Missing data from scheduled tumor assessments not performed will not be imputed. Evaluable tumor assessments are defined as those with an overall response of CR, PR, SD or PD. Data from non-evaluable (NE) tumor assessments will be used in the derivation of endpoints in accordance with Eisenhauer et al., 2009.

For IRC assessments, only the response assessments which are flagged as accepted after adjudication will be taken over to ADaM datasets and will be analyzed. In the case of a missing adjudication flag for a response assessment and the earliest image dates being equal, the assessment of reader 1 (the reader who completed baseline first) will be taken for analysis. Otherwise the assessment for the reviewer who reviewed the record with the earliest image date will be analyzed. Analyses of tumor sizes will be based only on assessments of the reader whose assessment was accepted at baseline.

For those participants in the monotherapy arm who switch to combination treatment, the latest available scan at the time of switch will be used to perform the baseline tumor assessment for the combination period. Only investigator assessments will continue after the switch and data will be collected in the usual eCRF pages dedicated to collection of tumor response. These evaluations will be called "Evaluation re-baseline", "Evaluation after re-baseline visit 1", etc. IRC assessments will stop at the first PD.

10 Study Participants

The subsections in this section include specifications for reporting participant disposition and study treatment/study discontinuations. Additionally, procedures for reporting protocol deviations are provided.

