If a respondent is missing any of the five domain scores, his or her NSCLC-SAQ total score will not be computed. If one of the Pain or Fatigue items is missing, the available item will be used as domain score; if both items are missing, the domain score will be set to missing.

Baseline, post-baseline and change from baseline values for each domain and for the total score will be summarized at each time point. The number and percentage of participants whose scores have improved, not changed or worsened will also be presented.

Listings of single items and sub-dimension scores over time will be provided.

Longitudinal analysis of change from baseline

A mixed-effect model repeated measures (MMRM) analysis will evaluate longitudinal change from baseline. This analysis will be performed on the combination arm (mFAS) only. The following PRO scores will be analyzed:

- Cough (NSCLC-SAQ; item 1)
- Pain (NSCLC-SAQ; items 2 and 3)
- Dyspnea (NSCLC-SAQ; item 4).

A distinct MMRM will be run for the T+, L+ and Combined (T+ and/or L+) participants in the combination arm. The model will include change from baseline as a dependent variable and analysis visit (as defined in Section 9.8) and baseline PRO score as covariates and baseline PRO score by analysis visit interaction to account for a non-constant baseline effect across visits.

An unstructured covariance matrix will be used to model the within-subject error. In case the fit fails to converge or if convergence is unreliable (e.g. problems to make hessian matrix positive definite), the best variance-covariance pattern will be chosen based on the model fit using the Akaike's Information Criterion among Toeplitz, first-order autoregressive and variance components. The model will use restricted maximum likelihood (REML) to provide an overall adjusted mean estimate that will estimate the average treatment effect over visits giving each visit equal weight. The Kenward-Roger approximation will be used to estimate the degrees of freedom. No p-values will be presented. No subgroup analysis planned.

Least square (LS) means estimates and corresponding 95% CIs will be presented overall, to provide an estimate of the treatment effect across visits, and at Day 85 (Week 12, i.e. Cycle 5 Day 1), Day 169 (Week 24, i.e. Cycle 9 Day 1), Day 253 (Week 36, i.e. Cycle 13 Day 1), Day 337 (Week 48, i.e. Cycle 17 Day 1), Day 421 (Week 60, i.e. Cycle 21 Day 1) and every 12 weeks thereafter. Additionally, a line plot will be produced.

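### After month 9 the fixed 126-day limit in PFS Table 6 censors a PD first seen at the next scheduled scan after one missed scan, and the text definition of the last evaluable assessment contradicts that table

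*SAP*

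**What the plan says.** Protocol 8.1 schedules scans every 6 weeks (±7 days) "following the Cycle 1 Day 1 visit until 9 months, and every 12 weeks" with a window of ± "14 days) thereafter according to RECIST Version 1.1". Both 9.4.1 of the protocol and the SAP apply one limit of 126 days throughout follow-up, to PD and to death, for PFS and DOR. Neither document derives it.

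The SAP describes the scan from which the 126 days run in two ways:

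- **PFS Table 6 (14.2.5):** an event counts if it is "Within 126 days after last response assessment of CR, PR or SD or start of treatment". A PD scan cannot be the reference.
- **PFS text (14.2.5) and DOR text (14.2.3):** "The last evaluable tumor assessment is defined as the last tumor assessment result that is not" NE. SAP 9.11 agrees: "Evaluable tumor assessments are defined as those with an overall response of CR, PR, SD or PD". Here a PD scan qualifies. DOR is censored when "date of PD/death - date of last evaluable tumor assessment > 126", and DOR has no table of its own.

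The CNS endpoints repeat the pattern. Sections 14.3.1.2 and 14.3.1.3 use the not-NE wording, while Table 9 for CNS PFS uses CR, PR, SD or non-CR/non-PD.

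**The concern.** A gap limit is meant to tolerate a set amount of missed follow-up. Here the tolerance changes with the calendar: the same 126 days that absorb a missed 6-weekly scan cannot absorb a missed 12-weekly one. The progressions lost are late ones, and the SAP reports PFS and DOR rates at 12, 15 and 18 months and every 3 months thereafter. None of the listed PFS or DOR sensitivity or supplementary analyses relaxes the limit, so a reader of the report could not see its effect.

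The two descriptions of the reference scan also give opposite event status to the same late PD. A programmer following the text and one following Table 6 would produce different PFS datasets. DOR, with no table, would depend on how its sentence is read.

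**Working it through.** **1. Calendar.** SAP 9.6 sets "1 month = 30.4375 days", so 9 months = 9 × 30.4375 = 273.9 days. Week 36 (252 days after Day 1) is inside that and week 42 (294 days) is outside, so week 36 is the last 6-weekly scan. SAP 14.2.7 shows the switch for questionnaires, which Protocol 8.1 puts on the same frequency: "Day 253 (Week 36, i.e. Cycle 13 Day 1), Day 337 (Week 48, i.e. Cycle 17 Day 1"). I take the scans as weeks 6, 12, …, 36, then 48, 60, 72 and so on.

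**2. Gaps.** The limit is 126 = 3 × 42 = 1.5 × 84 days. Gap = scheduled distance, minus or plus the two visit windows.

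| Last CR/PR/SD → next attended scan | Missed | Nominal (days) | Range (days) | PD under Table 6 |
|---|---|---|---|---|
| Week 24 → 36 | 1 | 84 | 70–98 | counts |
| Week 12 → 30 | 2 | 126 | 112–140 | depends on visit dates |
| Week 30 → 48 | 1 | 126 | 105–147 | depends on visit dates |
| Week 48 → 60 | 0 | 84 | 56–112 | counts |
| Week 36 → 60 | 1 | 168 | 147–189 | always censored |
| Week 48 → 72, and later | 1 | 168 | 140–196 | always censored |

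The limit fits a fully attended 12-weekly schedule (maximum 112 days). It tolerates one missed scan within the 6-weekly phase and none once two 12-week intervals are involved (minimum 140 days). Week 30 to week 48 is a borderline case.

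**3. Definitions.** Under the not-NE wording, a PD scan is the last result that is not NE. Date of PD minus date of last evaluable assessment is then 0 days, and no PD can exceed 126. Under Table 6 the reference is the last CR, PR or SD, and the gaps above apply.

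**4. Size.** The documents give no missed-scan rate, so I assumed 5%, 10% and 20%. Simulation settings: exponential PFS with median 8 or 12 months; 15% of events are deaths; administrative censoring uniform over 9–30 months; scans missed at random; no unscheduled or end-of-treatment scans; 200,000 participants per scenario. The 126-day limit is compared with 126 days before week 36 and 196 days from a week 36 or later reference scan.

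| Median (months) | Missed | Post-month-9 events discarded, 126 vs 126/196 | 18-month PFS, 126 vs 126/196 | 12-month PFS, 126 vs 126/196 |
|---|---|---|---|---|
| 8 | 5% | 7.6% vs 1.8% | 22.4% vs 21.8% (+0.6) | 37.4% vs 37.6% (−0.2) |
| 8 | 10% | 14.9% vs 4.7% | 23.4% vs 22.3% (+1.1) | 37.9% vs 38.3% (−0.4) |
| 8 | 20% | 29.2% vs 12.9% | 25.8% vs 23.5% (+2.2) | 39.3% vs 40.0% (−0.7) |
| 12 | 5% | 7.3% vs 1.5% | 37.0% vs 36.2% (+0.8) | 52.0% vs 52.2% (−0.2) |
| 12 | 10% | 14.6% vs 4.2% | 38.2% vs 36.7% (+1.5) | 52.6% vs 52.9% (−0.3) |
| 12 | 20% | 28.7% vs 12.0% | 41.0% vs 38.3% (+2.7) | 54.2% vs 54.6% (−0.4) |

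(Differences are taken before rounding.) Smaller runs of 12,000 per scenario scatter around these values, which is why I quote roughly 0.5–2.8 points at 18 months. Median PFS is nearly unchanged.

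The 12-month rate falls slightly because censoring a week-60 PD back to week 36 removes that participant from the risk set at week 48. Restoring the week 30 to week 48 PDs as well (a 147-day step) makes the 18-month difference slightly larger, 0.7–3.3 points, and the 12-month difference close to zero, 0.0–0.3 points.

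**The case against.** The strongest reply has four parts.

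- **Late PDs have other routes into the analysis.** SAP section 9 admits unscheduled visits to the efficacy endpoints, and after month 9 Protocol 8.1 requests an end-of-treatment scan if the last scan was at least 12 weeks earlier. A PD found that way 84–126 days after the reference, or a death within 126 days, is an event. This stands. A reader might infer that one missed scan always loses the progression; that is true only under Table 6 and only for a PD first seen at the next scheduled in-window scan. It also makes the simulated discard rates upper-end for scans missed at random.
- **The definition conflict is drafting, not two planned rules.** This stands as to intent. The PFS text carries the same not-NE sentence as DOR, so a reader who infers that PFS and DOR were planned under different rules goes too far. Table 6, Table 9 and the sentence on PDs preceded only by NE scans show that an earlier, non-PD assessment is meant. The wording as it stands can still be programmed either way.
- **The effect is small beside sampling error.** At n = 80 without censoring, the 95% half-width is 1.96 × √(p(1 − p)/80): about 9 points at p = 0.22 and 10.5 at p = 0.36. PFS and DOR are secondary and descriptive. This stands and limits the weight of the point, but the shift is systematic and more participants would not remove it.
- **The 126 days are in the protocol too.** This stands. Changing the limit departs from Protocol 9.4.1 and touches several SAP sections.

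**Conclusion.** The point holds in limited form and should be corrected. Under Table 6, once scans are 12-weekly, a PD first seen at the next scheduled scan after one missed scan is at least 140 days from the last CR, PR or SD and is always censored back. The same lapse within the 6-weekly phase is tolerated. Separately, the not-NE text would never censor a PD if taken literally and contradicts Table 6; the conflict recurs between the CNS PFS text and Table 9.

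The 18-month figure of roughly 0.5–2.8 points rests on assumed missed-scan rates of 5–20%, exponential PFS, misses at random and a 126/196-day comparator. Whether misses here would be linked to worsening cannot be settled from the documents.

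A reader might extend the upward bias to the 12-month rate. The working does not support that: relative to the 126/196-day limit the 12-month rate is slightly lower. ORR does not use the limit and is unaffected.

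**What to change.** 1. **Align the reference scan.** In SAP 14.2.3, 14.2.5, 14.3.1.2, 14.3.1.3 and the estimand table, define it as the last CR, PR or SD assessment before the event (for CNS, also non-CR/non-PD), or treatment start where there is none. This is needed even if 126 days is kept.
2. **Tie the limit to the schedule.** Use the next two scheduled scan intervals after the reference scan plus visit windows, never less than 126 days:
   - up to week 24: 42 + 42 + 7 + 7 = 98, so 126 applies;
   - week 30: 42 + 84 + 7 + 14 = 147;
   - week 48 onwards: 84 + 84 + 14 + 14 = 196. Week 36 gives 84 + 84 + 7 + 14 = 189, and 196 can serve for both.

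   A plain 126/196 split would still lose some PDs between week 30 and week 48. Record the departure from Protocol 9.4.1 in SAP section 7.
3. **Minimum alternative to step 2.** Keep 126 days as in the protocol and add a PFS and DOR sensitivity analysis that counts every PD and death regardless of gap.

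The cost is edits to several SAP sections and tables, a small programming change, and slightly less favourable late PFS and DOR rates. No additional data are needed.
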